3.4.1. Adverse Events

An AE is considered a treatment-emergent adverse event (TEAE) if the event starts on or after the first dosing day and time/start time, if collected, but before the last dose +30 days, or start of subsequent anticancer *drug* therapy minus 1 day, whichever occurs first. Any events that started prior to date of the first dose are not considered TEAEs. If an AE starts on the same day as date of the first dose, it will be considered treatment emergent unless the CRF data indicates otherwise via explicitly recording time for AE onset and treatment dosing.

Adverse events will be coded using current Medical Dictionary for Regulatory Activities (MedDRA). Severity of AEs will be graded using the NCI-CTCAE v 4.03 toxicity grading scale.

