5.3.1. Missing Dates

For purposes of data listings, dates will reflect only the information provided by the Investigator on the eCRF.

If start dates for adverse events or concomitant medications are completely missing a worst case approach will be taken whereby the events will be considered treatment emergent and the medications will be considered concomitant. If only partial information are available (eg, only a month and year or only a year) and the partial information provide sufficient information to indicate the dates are prior to the start of study treatment (eg, month/year less than month/year of first dose) then these will be considered to have started prior to treatment; otherwise a similar worst case approach will apply and these will be considered to have started after treatment.

Missing or Partial Death Dates

Missing or partial death dates will be imputed based on the last contact date:

- If the entire date is missing it will be imputed as the day after the date of last contact (see derivation of date of last contact in [Section 5.2.6](#)).
- If the day or month is missing, death will be imputed to the maximum of the full (non-imputed) day after the date of last contact and the following:
 - Missing day: 1st day of the month and year of death, or
 - Missing day and month: January 1st of the year of death.

Date of First and Last Dose of Study Treatment

No imputation will be done for first dose date.

Date of last dose of study drug, if unknown or partially unknown, will be imputed as follows:

- If the last date of study drug is completely missing and there is no End of Treatment eCRF page and no death date, the patient should be considered to be ongoing and use the cutoff date for the analysis as the last dosing date. **Note:** the study team should confirm that the patient is actively receiving dose at the time of the data cutoff.

- If the last date of study drug is completely or partially missing and there is EITHER an End of Treatment eCRF page OR a death date available (within the data cutoff date), then impute as follows:
 - If only Year is available and Year < Year of min (EOT date, death date), impute the date as 31DECYYYY.
 - If both Year and Month are available and Year = Year of min (EOT date, death date) and Month < Month of min (EOT date, death date), impute as last day of the month.
 - For all other cases, impute as min (EOT date, death date).

Date of Start of New Anticancer Therapy

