YYYY = Year of min [max(PD date +1, last dose of study treatment +1), end date of new anticancer therapy], AND

MMM = Month of min [max(PD date +1 day, last dose of study treatment +1 day), end date of new anticancer therapy]

THEN

imputed start date = min [max(PD date +1 day, last dose of study treatment +1 day), end date of new anticancer therapy];

ELSE IF

YYYY = Year of min [max(PD date +1, last dose of study treatment +1), end date of new anticancer therapy], AND

MMM > Month of min [max(PD date +1 day, last dose of study treatment +1 day), end date of new anticancer therapy].

THEN

imputed start date = 01 MMM YYYY;

ELSE IF

YYYY < Year of min [max(PD date +1, last dose of study treatment +1), end date of new anticancer therapy].

THEN

imputed start date = DAY (Last day of MMM) MMM YYYY;

ELSE IF

YYYY > Year of min [max(PD date +1, last dose of study treatment +1), end date of new anticancer therapy].

THEN

imputed start date = 01 MMM YYYY.

AE Dates

AE Onset Date:

If completely missing, the onset date will be set to first dose date if date of the first dose is less than AE stop date. Otherwise if date of the first dose is after AE stop date, then set the onset date to the earliest of non-missing AE stop date or informed consent date.

AE Stop Date:

If completely missing, the stop date will be imputed as the latest of the end of study date, death date, last dose date of the study treatment, or onset date.

Partial AE Date:

Partial AE date will be imputed based on the imputation rule for “Other Missing or Partial Dates”. If the AE onset date is imputed from a partial AE date and date of the first dose falls in the same month as the AE onset date, the following will be done:

- The AE onset date is reset to date of the first dose.

If AE stop date is imputed, and less than date of the first dose, set the AE stop date to date of the first dose.

Other Missing or Partial Dates

Imputation methods for other partial dates are as follows:

- If the day of the month is missing for a start date used in a calculation, the 1st of the month will be used to replace the missing date.
- If both the day and month are missing, the first day of the year is used.

- For stop dates, the last day of the month, or last day of the year is used if the day or day and month are missing, respectively.

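### SAP 5.3.1 gives two conflicting rules for an adverse event dated only by the year of first dose, and one of them could remove it from the TEAE tables

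*SAP*

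**What the plan says.** SAP 5.3.1 (Missing Dates) deals with incomplete AE start dates in two places.

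- **Opening paragraphs.** The rule names year-only dates as within its scope: "If only partial information are available (eg, only a month and year or only a year" (the quotation stops inside the SAP's bracket). An event is taken to precede treatment only if the known part of the date is enough to show it; "otherwise a similar worst case approach will apply and these will be considered to have started after treatment".
- **AE Dates, and Other Missing or Partial Dates.** Partial AE dates are sent to the generic partial-date rule. For a start date with only the year, "If both the day and month are missing, the first day of the year is used". One correction follows: an onset imputed in this way is moved to the first dose, but only on this condition: "date of the first dose falls in the same month as the AE onset date".

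SAP 3.4.1 defines TEAE status by date: "Any events that started prior to date of the first dose are not considered TEAEs". SAP 6.6.1 bases the AE analyses on TEAEs unless otherwise specified and flags the other events in listings. SAP 5.3 places imputation at the analysis dataset level. No sentence ranks the two parts of 5.3.1.

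**The concern.** The same record gets opposite answers within one section. An AE known to have begun in the year of first dose, with no month or day, is treatment emergent under the opening rule. Under the imputation rule it has a pre-treatment onset, unless dosing began in January.

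The imputation result also sits oddly with the rest of the section. A completely missing onset is set to the first dose date when the AE stop date is later than that date, so it is a TEAE. Learning the year, which is more information and does not point to a pre-dose start, moves the same event before treatment. The same-month reset appears meant to stop imputation from doing this, but it misses the year-only case.

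At stake is whether the TEAE tables are reproducible: two competent programmers could build different tables from this text. Incidence and severity of AEs is a primary endpoint of the Safety Lead-in and a secondary endpoint of the study (SAP 2.1).

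**Working it through.** The plan gives no figure to reproduce here. The check traces the rules over every possible first-dose date.

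**Inputs**
- Year-only onset becomes 1 January of that year (SAP 5.3.1, Other Missing or Partial Dates).
- Reset to first dose if first dose is in the same month as the imputed onset (SAP 5.3.1, Partial AE Date).
- An onset before first dose is not a TEAE (SAP 3.4.1).
- Worst case: a partial date counts as pre-treatment only if it shows this (SAP 5.3.1, opening paragraphs).
- Screening may not exceed 28 days (Protocol 7.1), and AE collection begins at consent (Protocol 7.4.1).

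**One record.** First dose 15 June 2020, AE onset recorded as 2020.
1. The imputed onset is 1 January 2020, which is 166 days before first dose.
2. January is not June, so there is no reset.
3. The imputed onset precedes first dose, so by date the event is not a TEAE.
4. Under the opening rule, the year 2020 does not show a start before June 2020, so the event is a TEAE.

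**All first-dose dates, year-only onset in the first-dose year**

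| Year length | First-dose dates | TEAE by worst-case rule | Non-TEAE by imputed date |
|---|---|---|---|
| 365 days | 365 | 365 | 365 − 31 = 334 (91.5%) |
| 366 days | 366 | 366 | 366 − 31 = 335 (91.5%) |

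The 31 January dates are saved by the same-month reset. Every date from 1 February to 31 December is not.

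**Can another rule rescue the record?** SAP 5.3.1 suspends the generic rules only when they produce a negative duration. Moving an onset earlier lengthens the duration, so that clause does not apply.

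**Is the imputed date plausible as an onset on study?** The smallest gap is from 1 January to 1 February, 31 days, which exceeds 28. In all 334 cases the imputed onset lies before a single screening period could have opened.

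**Other partial dates.** For month-and-year onsets the two rules agreed in every combination tried (first doses on the 1st, 15th and 28th of each month against each onset month of the same year: 0 disagreements). For year-only onsets, a year before the first-dose year is pre-treatment under both rules, and a later year is after first dose under both. The conflict is confined to the first-dose year.

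**Size of one record.** If the event is the patient's only one under its preferred term, losing it lowers that term's rate by 1/9 = 11.1 percentage points in a lead-in of 9 patients, or 1/50 = 2.0 points in a cohort of 50.

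**The case against.** The strongest reply is that the two rules can be read together. The opening paragraphs are the only text in 5.3.1 that speaks of treatment-emergent status for incomplete AE dates, and they cover year-only dates. The generic rules speak of dates used in calculations and carry a safeguard about durations. On that reading the opening rule sets the flag, the imputed date serves only for durations or study day, and no TEAE is lost.

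This reading is available and the SAP does not exclude it. A reader might infer that the plan drops these events, or that every year-only onset is misclassified; the documents do not support either statement. Both need the imputed date to override the opening rule, which is nowhere stated. Some such events may also be genuine pre-dose events, since AEs are collected from consent.

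Three further points stand. The 91.5% is a share of possible first-dose dates, not of events or patients. AEs are assessed continuously (Protocol 1.3), so a year-only onset should be unusual. Any event excluded from the tables would still appear in the listings, with the date as entered.

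The reply does not remove the conflict. The TEAE definition is date-based, imputation is done in the analysis datasets, and the resets to first dose for same-month and completely missing onsets make most sense if imputed dates were meant to feed the flag. Both readings are reasonable, and the SAP does not choose between them.

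**Conclusion.** SAP 5.3.1 contradicts itself for year-only AE onsets in the year of first dose, with no stated precedence. For first doses from February to December the imputed onset precedes treatment, and the event could be lost from the TEAE tables if that date drives the flag. Against the worst-case rule, any difference for these records runs toward fewer TEAEs, which is the direction such a rule exists to prevent.

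The point is minor. Neither document gives the number of year-only onsets; that it is small is an assumption, and no effect on any TEAE percentage has been shown. The brain metastasis response rate does not depend on AE dates. The correction is still worth making, because a written imputation rule contradicts the section's own worst-case rule and is less conservative than the rule for an onset with no date at all.

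**What to change.** State in SAP 5.3.1 that the worst-case rule in the opening paragraphs determines TEAE status for partial AE dates. Then align the imputation by adding under Partial AE Date:

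> If only the year of AE onset is known and it equals the year of first dose, set onset to the date of first dose; if the AE stop date is before first dose, apply the existing rule for completely missing onset dates.

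The first statement settles which rule governs. The second makes the dataset date agree with it and says what to do when the event ended before dosing. With both in place, and a stop date that is not before first dose, the number of first-dose dates giving a pre-treatment onset falls from 334 of 365 to 0 of 365. The cost is two sentences in the SAP and about one line of code, with no change to data collection.

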5.3.2. Missing Pharmacokinetic Data

Deviations, Missing Concentrations and Anomalous Values

In summary tables and plots of geometric mean profiles, concentrations will be set to missing if one of the following cases is true:

- A concentration has been reported as ND (ie, not done) or NS (ie, no sample);
- A deviation in sampling time is of sufficient concern or a concentration has been flagged as anomalous by the clinical pharmacologist.

Summary statistics will not be presented at a particular timepoint if more than 50% of the data are missing. For analysis of pharmacokinetic concentrations, no values will be imputed for missing data.

5.3.3. Missing Biomarker Data

No missing data will be imputed.

6. ANALYSES AND SUMMARIES

The primary analysis will take place after all patients in the Efficacy Set meet the following criteria:

- had at least 2 post-baseline tumor assessments, or discontinued from the study or had disease progression/death at any time on the study;
- all patients with an initial brain metastasis response have been followed up for at least 6 months.

Efficacy analyses will be performed using the Efficacy Set. Key efficacy analyses will also be repeated using the FAS. All safety analyses will be performed using the Safety Set.

6.1. Primary Endpoints

6.1.1. Safety Lead-in

The number and proportion of patients experiencing DLTs during Cycle 1 will be summarized by SOC and PT based on maximum toxicity grade. Analyses of DLT will be performed on Dose-determining Set.

All DLTs and their attributes will be presented in data listings sorted by patient identifier, AE and date of onset of the AE.

6.1.2. Phase 2

Main Analysis:

BMRR will be calculated by dividing the number of patients with a BOR of confirmed CR or confirmed PR in brain metastasis by the number of patients in the Efficacy Set in the respective cohort. The corresponding exact Clopper-Pearson 2-sided 90% CI and 95% CI will be calculated.

BOR is defined as the best response recorded from date of the first dose of study treatment until progression by Investigator assessment at each time point. Only tumor assessments performed before the start of any subsequent anticancer therapies will be considered in the assessment of BOR. Clinical deterioration or clinical progression noted on the End of Study completion eCRF will not be considered as documented disease progression. BOR will be determined according to the following rules:

- CR = at least two determinations of CR at least 4 weeks apart and documented before progression and start of new anticancer therapy.
- PR = at least two determinations of PR or better (and not qualifying for a CR) at least 4 weeks apart and documented before progression and start of new anticancer therapy.
- SD (for patients with at least one measurable lesion at baseline)= at least one SD assessment (or better and not qualifying for CR or PR) ≥ 6 weeks after date of the first dose and before progression and start of new anticancer.
- Non-CR/Non-PD (for patients with only non-target disease at baseline) = at least one Non-CR/Non-PD assessment (or better and not qualifying for CR or PR) ≥ 6 weeks after date of the first dose and before progression and the start of new anticancer therapy.
- PD = progression ≤ 16 weeks after date of the first dose (and not qualifying for CR, PR or SD).
- Not Evaluable (NE) = all other cases.

The frequency (number and percentage) of patients with BOR in brain metastasis of CR, PR, SD, PD, non-CR/non-PD (applicable only to patients with non-measurable disease at baseline), and NE will be tabulated.

Patients with a BOR in brain metastasis of “Not Evaluable” based on confirmed responses will be summarized by reason for having unknown status. The following reasons will be used:

- No adequate baseline assessment.

- No post-baseline assessments due to early death (ie, death ≤ 16 weeks after the start date).
- No post-baseline assessments due to COVID-19 (ie, patients miss tumor assessment visits due to COVID-19 pandemic).
- No post-baseline assessments due to other reasons.
- All post-baseline assessments have overall response NE.
- New anticancer therapy started before first post-baseline assessment.
- SD of insufficient duration (< 6 weeks after date of the first dose without further evaluable tumor assessments).
- PD > 16 weeks after date of the first dose (ie, tumor assessment of PD was > 16 weeks after date of the first dose and there was no tumor assessment in between).

Special and rare cases where BOR is NE due to both SD of insufficient duration (SD < 6 weeks after date of the first dose) and late PD (PD > 16 weeks after date of the first dose) will be classified as “SD of insufficient duration”.

A figure for duration of exposure and BOR in brain metastasis (confirmed) per mRECIST v1.1 will be created.

A waterfall plot will be created to show the best percentage change from baseline in the sum of longest diameters of all target brain metastases. Patients with baseline and at least one post-baseline brain metastasis assessment will be included in the waterfall plot.

Individual brain metastasis measurements, overall brain metastasis response assessments per mRECIST v1.1 and target and non-target response by timepoint per mRECIST v1.1 will be listed by patient and assessment date.

Sensitivity/Supplementary Analyses

- BMRR based on confirmed + unconfirmed response (CR or PR) in brain metastasis will be calculated along with corresponding exact Clopper-Pearson 2-sided 95% CI.
- BMRR based on confirmed response (CR or PR) in brain metastasis will be calculated using the FAS.

6.2. Efficacy Secondary Endpoints

6.2.1. Extracranial Response Rate

Extracranial response rate will be calculated by dividing the number of patients with a BOR of CR or PR in extracranial lesions by the number of patients in the Efficacy Set in the respective cohort. The corresponding exact Clopper-Pearson 2-sided 95% CI will be calculated.

Details for the determination of BOR are provided in [Section 6.1.2](#).

Two sets of extracranial response rates will be summarized, one based on confirmed responses and one based on confirmed + unconfirmed responses in extracranial lesions.

Patients with extracranial response rate ‘Not Evaluable’ will be summarized by reason for having unknown status (see [Section 6.1.2](#) for reasons).

A figure for duration of exposure and best overall extracranial response (confirmed) per RECIST v1.1 will be created.

A waterfall plot will be created to show the best percentage change from baseline in the sum of longest diameters of target extracranial lesions. Patients with baseline and at least one post-baseline extracranial tumor assessment will be included in the waterfall plot.

Individual extracranial lesion measurements, overall extracranial response assessments, and target and non-target response by timepoint per RECIST v1.1 will be listed.

6.2.2. Global Response Rate

Global response rate will be calculated by dividing the number of patients with a BOR of CR or PR in both brain and extracranial lesions by the number of patients in the Efficacy Set in the respective cohort. The corresponding exact Clopper-Pearson 2-sided 95% CI will be calculated.

Details for the determination of BOR are provided in [Section 6.1.2](#).

Two sets of global response rates will be summarized, one based on confirmed responses and one based on confirmed + unconfirmed responses in global (brain and extracranial) lesions.

Patients with global response rate ‘Not Evaluable’ will be summarized by reason for having unknown status (see [Section 6.1.2](#) for reasons).

A figure for duration of exposure and best overall global response (confirmed) will be created.

A waterfall plot will be created to show the best percentage change from baseline in the sum of longest diameters of all target lesions (brain and extracranial). Patients with baseline and at least one post-baseline tumor assessment will be included in the waterfall plot.

Overall global response assessments and timepoint response will be listed by patient and assessment date.

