8.4.2.2. Global Response Rate

Global response rate is defined as the proportion of patients with a best overall response of CR or PR per Investigator assessment for brain metastasis and extracranial lesions according to mRECIST v1.1 and RECIST v1.1, respectively. Details of best overall response are specified in [Appendix 6](#).

ORR will be calculated with exact two-sided 95% CIs.

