Appendix 6. Criteria for Evaluation of Global Response

This appendix provides definitions for global assessment of target and non-target lesion(s).

Evaluation of Target Lesions

Target lesion response is based on all (i.e., brain and extracranial) target lesions, up to a total of 10 lesions. The sum of longest diameters of all target lesions will be used to determine response. Definitions for assessment of response for target lesion(s), based on mRECIST v1.1 for brain lesion and RECIST v1.1 for extracranial lesions, are as follows:

Complete Response (CR): Disappearance of all target lesions. Any pathological lymph nodes must be < 10 mm on the short axis.

Partial Response (PR): At least a 30% decrease in the sum of the diameters of target lesions, taking as a reference the baseline sum of the diameters (e.g., percent change from baseline).

Stable Disease (SD): Neither sufficient shrinkage to qualify for PR nor sufficient increase to qualify for PD.

Progressive Disease (PD): At least a 20% increase in the sum of the diameters of target lesions, taking as a reference the smallest sum of diameters recorded since the treatment started (i.e., percent change from nadir, where nadir is defined as the smallest sum of diameters recorded since treatment start). In addition, the sum must have an absolute increase from nadir of at least 5 mm.

Not Applicable (NA): No extracranial target lesions at baseline.

Not Evaluable (NE): Cannot be classified by 1 of the 5 preceding definitions.

Special Notes on the Assessment of Target Lesions

If lymph nodes are documented as target lesions, the short axis is added to the sum of the diameters (i.e., sum of diameters is the sum of the longest diameters for non-nodal lesions and the short axis for nodal lesions). When lymph nodes decrease to non-pathological size (i.e., short axis < 10 mm), they should still have a measurement reported in order not to overstate progression.

If at a given assessment time point all target lesions identified as baseline are not assessed, the sum of diameters cannot be calculated for purposes of assessing CR, PR or SD, or for use as the nadir for future assessments. However, the sum of the diameters of the assessed lesions and the percent change from nadir should be calculated to ensure that progression has not been documented. If an assessment of PD cannot be made, the response assessment should be NE.

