
 Further evaluate the antitumor activity of encorafenib + binimetinib combination therapy in patients with BRAFV600-mutant melanoma who have asymptomatic brain metastasis. 	
 Extracranial response rate per RECIST v1.1. Global response rate (brain metastasis response per mRECIST v1.1 and extracranial response per RECIST v1.1). DCR: 
 for brain metastasis response per mRECIST v1.1; for extracranial response per RECIST v1.1; for global response (brain metastasis per mRECIST v1.1 and extracranial per RECIST v1.1). DOR: 
 for brain metastasis response per mRECIST v1.1; for extracranial response per RECIST v1.1; for global response (brain metastasis per mRECIST v1.1 and extracranial per RECIST v1.1). PFS: 
 for brain metastasis per mRECIST v1.1; for global assessment (brain metastasis per mRECIST v1.1 and extracranial disease per RECIST v1.1). BMRR per mRECIST v1.1 for Safety Lead-in only.

 Evaluate the efficacy of encorafenib + binimetinib combination therapy as measured by OS in patients with BRAFV600-mutant melanoma who have asymptomatic brain metastasis. 	
 OS.

 Further evaluate the safety profile of encorafenib + binimetinib combination therapy in patients with BRAFV600-mutant melanoma who have asymptomatic brain metastasis. 	
 Incidence and severity of AEs graded according to the NCI CTCAE version 4.03 and changes in clinical laboratory parameters, vital signs and ECGs.

 Characterize the PK of encorafenib and its metabolite LHY746, and binimetinib and its metabolite AR00426032. 	
 Plasma concentration-time profiles and PK parameter estimates for encorafenib and its metabolite LHY746, and binimetinib and its metabolite AR00426032.
CCI [REDACTED]	[REDACTED]
[REDACTED]	[REDACTED]
[REDACTED]	[REDACTED]
[REDACTED]	[REDACTED]
[REDACTED]	[REDACTED]

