3.2.2.2. Global Response Rate

Global response rate is defined as the proportion of patients with a BOR of confirmed CR or confirmed PR by Investigator assessment in brain metastasis and extracranial lesions per mRECIST v1.1 and RECIST v1.1, respectively.

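### SAP 6.2.2 counts global responders by response in both compartments, while Protocol Appendix 6 derives one global response from the pooled lesion sum; read literally, the two rules give different counts

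*SAP*

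**What the plan says.** **SAP 6.2.2, calculation sentence.** The numerator is patients with "a BOR of CR or PR in both brain and extracranial lesions by the number of patients in the Efficacy Set" of the respective cohort. For the derivation of BOR the section points to SAP 6.1.2, which gives rules for a series of time-point responses but none for combining two compartments.

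**SAP 6.2.2, remaining text.** The confirmed and unconfirmed summaries concern "responses in global (brain and extracranial) lesions". The waterfall plot uses the summed diameters of all target lesions, brain and extracranial together. A figure and a listing refer to a single overall global response.

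**SAP 2.1 and 3.2.2.2.** The endpoint is listed as "Global response rate (brain metastasis response per mRECIST v1.1 and extracranial response per RECIST v1.1" and defined "by Investigator assessment in brain metastasis and extracranial lesions per mRECIST v1.1 and RECIST v1.1, respectively". Neither sentence says how the compartments are combined.

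**Protocol 8.4.2.2.** The definition names the two criteria "for brain metastasis and extracranial lesions according to mRECIST v1.1 and RECIST v1.1, respectively", and then says "Details of best overall response are specified in" Appendix 6.

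**Protocol Appendix 6.** Target response rests on all brain and extracranial target lesions, up to 10: "The sum of longest diameters of all target lesions will be used to determine response". Non-target lesions are also taken together. Table A4 turns target, non-target and new-lesion status into one global response per time point. The target categories include "Not Applicable (NA): No extracranial target lesions at baseline", but Table A4 has no row for target = NA.

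**The concern.** Two separate compartment responses and one pooled response are different rules, and the sentence a programmer would code is the one that departs from Appendix 6.

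The brain-only patient is a foreseeable case. Inclusion criterion 6 (Protocol 5.1) requires a brain lesion, no inclusion criterion requires extracranial disease, and Appendix 6 itself provides for patients without extracranial target lesions. Such patients stay in the Efficacy Set denominator but, on the literal sentence, cannot enter the numerator.

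At stake is whether the reported rate is the one the protocol defines. SAP 6.2.3 and 6.2.4 refer to global response without saying how it is derived, so global disease control rate (DCR) and duration of response (DOR) depend on the same choice.

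**Working it through.** The documents give no planned figure for the global response rate. The only powered Phase 2 figure is for BMRR: at least 21 responders of 50, null 30%, alternative 50%. The exact binomial gives a one-sided alpha of 0.0478 and power of 0.8987, matching the stated 5% and approximately 90%. It does not use the global response.

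**1. Patient with disease in both compartments** (constructed lesion sizes; no non-target progression, no new lesion, findings confirmed)
- Brain 20 to 20 mm: (20 - 20)/20 = 0%, SD.
- Extracranial 60 to 36 mm: (36 - 60)/60 = -40.0%, PR.
- Pooled 80 to 56 mm: (56 - 80)/80 = -30.0%, target-lesion PR under Appendix 6.
- Appendix 6: responder. Literal SAP sentence: not a responder.

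**2. The reverse case** (same baselines, constructed course)
- Two early assessments: brain 14 mm, extracranial 60 mm. Brain (14 - 20)/20 = -30.0%, a confirmed PR. Pooled (74 - 80)/80 = -7.5%.
- Two later assessments: brain 16 mm, extracranial 42 mm. Brain has regrown by (16 - 14)/14 = 14.3%, which is not PD. Extracranial (42 - 60)/60 = -30.0%, a confirmed PR. Pooled (58 - 80)/80 = -27.5%.
- Literal SAP sentence: responder. Appendix 6: never a PR.

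So in these patients the discrepancy has no fixed sign. Its size cannot be computed, because lesion sizes and the correlation between compartments are not in the documents.

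**3. Brain-only patients.** Let f be their share of the Efficacy Set and r their response rate under Appendix 6. The literal sentence caps the rate at 1 - f and lowers it by f × r. The documents do not give f, so 10% to 30% is an assumption. For r, the BMRR null (30%) and alternative (50%) in Protocol 8.1 are borrowed as reference values.

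| f | ceiling 1 - f | loss at r = 30% | loss at r = 50% |
|---|---|---|---|
| 10% | 90% | 3.0 points | 5.0 points |
| 20% | 80% | 6.0 points | 10.0 points |
| 30% | 70% | 9.0 points | 15.0 points |

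**4. One cohort of 50** with f = 20% and r = 50%: 10 brain-only patients, of whom 5 respond. Assume 20 responders by either rule among the other 40.
- Appendix 6: (20 + 5)/50 = 50.0%, exact 95% CI 35.5% to 64.5%.
- Literal SAP sentence: 20/50 = 40.0%, exact 95% CI 26.4% to 54.8%.

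**The case against.** The strongest reply is that SAP 6.2.2 can be read as pooled. It speaks of one BOR, and its waterfall plot, figure and listing all need a single global response. Protocol 8.4.2.2 already settles the derivation by pointing to Appendix 6. The SAP may also modify protocol methods for an endpoint of this rank, and no hypothesis is attached to it.

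Much of this stands. Pooling was probably intended. But the calculation sentence says otherwise, SAP 6.2.2 cites SAP 6.1.2 and not Appendix 6, and the visible text does not present the sentence as a deliberate change of definition.

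A reader might infer more than the documents support:

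- *That Protocol 8.4.2.2 is itself ambiguous.* Naming two criteria is compatible with pooling. Appendix 6 applies each set of criteria to its own lesions inside a pooled definition, and the cross-reference decides the matter.
- *That Appendix 6 leaves brain-only patients unclassified.* An eligible brain-only patient has a brain target sum, which fits the CR, PR, SD or PD rows of Table A4. The NA label without a row is untidy drafting that one sentence can clear up.
- *That the SAP rule always lowers the rate.* This holds for brain-only patients. Step 2 of the working shows the opposite in a patient with disease in both compartments.
- *That the whole-set denominator for the extracranial rate in SAP 6.2.1 is an error.* It follows the default analysis set in Protocol 8.3. A rate among patients with extracranial disease would be a useful addition, no more.

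**Conclusion.** The calculation sentence in SAP 6.2.2 conflicts with the derivation in Protocol Appendix 6 and, if programmed literally, misclassifies some patients. From brain-only patients alone the rate falls by 3 to 9 points at r = 30% and by 5 to 15 points at r = 50%. These figures rest on an assumed brain-only share of 10% to 30% and on response rates borrowed from the BMRR hypotheses, so they show scale and are not estimates for this trial. For patients with disease in both compartments neither size nor net direction can be stated.

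The statement that a brain-only patient can never be a global responder is true of the literal sentence only; it does not describe a settled intention of the plan. The endpoint is secondary and descriptive. BMRR, its 21 of 50 rule and its power are unaffected. The point deserves correction because it changes a reported result and costs almost nothing to repair.

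**What to change.** - In SAP 6.2.2, redefine the numerator as patients with a best overall global response of CR or PR per Protocol Appendix 6. Keep the full Efficacy Set as denominator.
- State that patients without extracranial lesions at baseline are classified on their brain lesions, so that the target = NA label does not leave them without a row in Table A4.
- Use the same definition for global DCR and DOR (SAP 6.2.3 and 6.2.4).
- Protocol 8.4.2.2 needs no change.
- Optional: beside the whole-set extracranial rate, report the rate among patients with extracranial disease at baseline. With an assumed 22 responders and 10 of 50 patients without such disease, this puts 22/40 = 55.0% (exact 95% CI 38.5% to 70.7%) next to 22/50 = 44.0% (30.0% to 58.7%).

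The cost is SAP wording and programming, best settled before database lock. No new data are needed and the sample size does not change. The optional rate has a somewhat wider interval: 32.3 against 28.8 percentage points in the example.
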